### **13.3 Monitoring for Toxicity and Response**

**13.3.1** 21 additional patients will be enrolled at IL-2+HCQ 600 mg/day on this revised protocol. If one or more TLTs are observed, treatment will be de-escalated to IL-2+HCQ 400 mg/day.

**13.3.2** The number of overall partial and complete responses (**Table 8**) will be compared to the stopping rule described in Table 10 by the UPCI Multi-Center DSMC after every three patients become evaluable for response. For each number of evaluable patients in the left-hand columns, if the number of complete responses is less than or equal to the number in the right-hand column, the trial will be halted for lack of efficacy. The trial is derived from a Bayesian beta-binomial model with the prior determined by the number of complete responses observed in the high-dose arm of the randomized trial described in Section 2.3 (8/95). The values correspond to P (partial and complete response rate < 0.10) > 0.8.

# Patients	#Responses
18	0
21	1
24	1
27	1
30	2
33	2
36	2

*Table 8.* Monitoring rule for complete response. For the given number of patients in Column 1, if the number of partial or complete responses is less than or equal to the number in Column 2, the trial is halted for lack of efficacy.

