### **2.18 Early experience with the regimen.**

The first five patients were treated with 600mg of Hydroxychloroquine with one patient deemed a complete response. Out of the 13 patients treated with combination HCQ/IL-2 therapy using 1200 mg of Hydroxychloroquine, two patients experienced pronounced hypotension and tachycardia. Furthermore, one patient died from pulmonary emboli, not attributed to therapy. The cardiac events are consistent with IL-2 toxicities, but were observed somewhat earlier in the course of treatment. For that reason we are accruing another 21 patients to assess response in addition to the first five patients at the lower 600mg/d dose.

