## 13.0 STATISTICAL ANALYSIS AND STUDY SIZE

### 13.1 Objectives and Design

The primary objective of this Phase II trial is to estimate the proportions of patients with metastatic RCC treated with high-dose IL-2 combined with hydroxychloroquine experiencing complete response, or any response. The secondary objectives are to compare response, time to progression and survival to historical data to determine the toxicity of the treatment regimen, to evaluate PD, and to examine correlative science endpoints. Disease endpoints are defined in Section 10.

The accrual goal is 39 participants. All study participants will receive the same high-dose IL-2 treatment, which is considered standard of care. The initial dose of HCQ will be 600 mg/day for all patients. If no limitations on additional dosing (treatment-limiting toxicities [TLTs], as defined in Section 9.2), dosing will continue at 600mg/d, otherwise, HCQ will de-escalate to 400 mg/d. Toxicity and response will be monitored after every three patients (Section 13.4), and will be stopped if the probability that treatment with IL-2+HCQ is excessively toxic or ineffective. The study may be opened more broadly to additional Cytokine Working Group sites whenever sufficient evidence has accrued that treatment with IL-2+HCQ is no more toxic or less effective than treatment with IL-2 alone.

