### 13.4 Justification of Design

The primary objective of this study is to estimate the clinical response rate of patients with metastatic RCC treated with IL-2 combined with hydroxychloroquine at 600mg/d. Assuming no TLTs occur and the trial is not closed early for toxicity or inadequate response (Section 13.3.2), there will be 39 patients available for this objective. A 95% exact binomial confidence interval on 5 responses out of 39 patients (expected if the addition of HCQ to IL-2 doubles the historic proportions of CR ~ 8%) would have width equal to 0.27 (0.07,0.34). For the secondary endpoints of OS and PFS, if patients are recruited over 15 months, observed for 15 additional months, and the true median survival is 16 months, then the expected width of the 95% confidence interval for median survival is 12.8 months.

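### Section 13.4 counts 39 patients for the complete-response estimate at 600 mg/d, but the plan's own counts give at most 26 at that dose, and the printed exact interval for 5/39 is wrong

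*Combined protocol and SAP*

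**What the plan says.** The primary objective (Section 1.1, repeated in 13.2.1) is the proportion with CR at one named HCQ dose, 600 mg/d. Section 13.4 restates that dose and, under the condition "Assuming no TLTs occur and the trial is not closed early for toxicity or inadequate response", says "there will be 39 patients available for this objective". It then gives an exact 95% interval for 5 responses in 39 as (0.07, 0.34), width 0.27. Section 13.1 agrees on the total, "The accrual goal is 39 participants", and adds "The initial dose of HCQ will be 600 mg/day for all patients".

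Section 2.18 gives the head count by dose. Five patients were treated at 600 mg. A further group is described by "Out of the 13 patients treated with combination HCQ/IL-2 therapy using 1200 mg of Hydroxychloroquine". After early cardiac events in that group, the plan is: "we are accruing another 21 patients to assess response in addition to the first five patients at the lower 600mg/d dose". Section 13.3.1 and the Summary also give 21 for the new 600 mg/d group.

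The analysis sets are defined without a dose. Section 11 takes every eligible patient with at least one week of IL-2 into the main response analysis. Section 4.4 adds two weeks of oral HCQ at an unnamed dose.

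On later dose changes, Section 13.3.1 says "If one or more TLTs are observed, treatment will be de-escalated to IL-2+HCQ 400 mg/day", and Section 13.1 says that without limiting toxicity "dosing will continue at 600mg/d, otherwise, HCQ will de-escalate to 400 mg/d".

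**The concern.** This is an estimation trial, so the number of patients at the named dose and the resulting interval width are the whole sample-size justification. If 39 is taken at face value, Section 13.4 overstates that number by half (39/26 = 1.5).

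The number also bears on who is analysed. Sections 11 and 4.4 contain nothing that removes a patient treated at 1200 mg, and Section 13.4 attaches 39 to the 600 mg/d objective. An analyst who follows both would put the 1200 mg patients into the primary proportion. One who follows the objective's wording would leave them out. In an open-label single-arm trial, that choice should not remain open once responses are known.

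**Working it through.** **Inputs.** 5 treated at 600 mg and 13 at 1200 mg (2.18); 21 more at 600 mg/d (2.18, 13.3.1, Summary); 39 available, 5 responses, historic CR about 8% doubled, 95% exact binomial interval (13.4).

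**1. The plan's own interval.** The exact (Clopper-Pearson) limits for x responses in n are:

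- lower = 2.5% quantile of Beta(x, n − x + 1)
- upper = 97.5% quantile of Beta(x + 1, n − x)

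For 5/39 these are 0.043 and 0.274, width 0.231. The printed (0.07, 0.34) does not reproduce. Other methods on 5/39 do not give it either: Wilson 0.056 to 0.267, Agresti-Coull 0.051 to 0.272, Jeffreys 0.051 to 0.258, Wald 0.023 to 0.233. A search over n = 15 to 59 found one exact interval that rounds to the printed limits: 6/35 (0.066 to 0.337, width 0.271).

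**2. Head count.**

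- At 600 mg/d: 5 + 21 = 26.
- All doses: 5 + 13 + 21 = 39.

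On these counts, 39 is reached only if the 13 patients at 1200 mg are included. They would then be 13/39 = 33% of the total.

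**3. Precision on a like-for-like basis.** Doubling 8% gives 16%. The expected counts are 0.16 × 39 = 6.24, nearest integer 6, and 0.16 × 26 = 4.16, nearest integer 4.

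| Responses/N | Proportion | Exact 95% CI | Width |
|---|---|---|---|
| 5/39 (count used in 13.4) | 0.128 | 0.043 to 0.274 | 0.231 |
| 6/39 | 0.154 | 0.059 to 0.305 | 0.247 |
| 3/26 | 0.115 | 0.025 to 0.302 | 0.277 |
| 4/26 | 0.154 | 0.044 to 0.349 | 0.305 |
| 5/26 | 0.192 | 0.066 to 0.394 | 0.328 |

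At the same observed proportion (6/39 and 4/26 are both 0.154), the width rises by 0.305 − 0.247 = 0.058.

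**4. The monitoring table.** Table 8 has looks at 18, 21, 24, 27, 30, 33 and 36 patients. Its thresholds (0, 1, 1, 1, 2, 2, 2) reproduce with a Beta(8, 87) prior and the rule P(rate < 0.10) > 0.8. A group of at most 26 reaches only the looks at 18, 21 and 24. The four looks from 27 to 36 need a larger group, such as all 39.

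**The case against.** The strongest reply is that the estimate is already restricted by dose. Sections 1.1, 13.2.1 and 13.4 all name 600 mg/d, and Section 2.18 identifies the intended patients as the first five plus 21 more. Sections 11 and 4.4 are general evaluability rules and need not repeat the dose. On this view the 39 is simply an accrual figure that was never updated, and Section 13.1 pairs it with a 600 mg start for everyone.

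Much of this stands. The plan does name a dose, and 5 + 21 is the best reading of the intended set. But the reply concedes that the figure in 13.4 is wrong. Because 13.4 applies the 600 mg/d wording to 39 patients, that wording alone cannot be relied on to exclude anyone. The condition about no limiting toxicity does not explain the gap either: it concerns future de-escalation, whereas the 13 have already been treated.

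A reader might also infer from 13.1 and 13.3.1 that later enrollees will start at 400 mg/d and shrink the 600 mg/d group further. The documents do not support that. Section 13.1 starts all patients at 600 mg/d and no section starts anyone at 400. Section 9.2 limits HCQ changes to individuals whose toxicity is judged likely due to HCQ or the combination, and Sections 6.3.1.1 and 9.4 describe reductions within a patient. These favour a patient-level rule, although the wording of 13.3.1 alone does not settle it.

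Patients who start at 600 mg/d and are later reduced are not at issue. Section 11 already says that departures in drug administration do not exclude a patient from the response analysis.

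**Conclusion.** The point holds as a stated figure that is wrong and a set definition that needs one more line. At most 26 patients can have started at 600 mg/d, not 39. The exact width at about 16% CR is 0.31 (4/26) rather than 0.25 (6/39), and the printed interval for 5/39 is wrong whichever N is used. The loss of precision is modest; the error in the denominator of the primary estimate is not.

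This assumes that the 5 and the 13 in Section 2.18 are different patients, that all 21 are enrolled, and that all 26 are evaluable under Section 11. Any shortfall lowers the 26.

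Three stronger readings go beyond the documents:

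- That the plan sets no dose condition at all. The objective names 600 mg/d in three places; only the evaluability rules omit it.
- That 13 of the 39 are known to be 1200 mg patients. The sum fits exactly, but the plan does not state the derivation, and an outdated accrual figure is also possible.
- That pooling would bias the CR proportion in a known direction. No CR count is given for the 1200 mg patients, so neither the size nor the direction of any bias can be stated.

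**What to change.** - **13.2.1:** define the primary CR set as all patients evaluable under Section 11 who began HCQ at 600 mg/d, keeping those with later reductions. Report the 1200 mg patients separately.
- **13.4:** replace 39 with at most 26 (5 + 21). Replace the printed interval with a matching one, for example 4/26, exact 95% CI 0.044 to 0.349, width 0.31.
- **13.1:** explain the accrual goal of 39 as 26 at 600 mg/d plus 13 at 1200 mg if that is its source, and reword the sentence on the initial dose to fit. Otherwise correct the goal.
- **13.3.2 and Table 8:** state which patients are counted. If only 600 mg/d starters count, the looks at 27 to 36 fall away. If all doses count, say that monitoring runs on a wider group than the primary analysis.
- **13.3.1 (optional):** add a phrase saying whether de-escalation applies to the affected patient.

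The cost is wording, plus a decision on Table 8. No patients or procedures are added. The downside is a less favourable stated precision: 0.31 against 0.25 like for like, or against the printed 0.27, which was itself miscalculated.

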## 9.2 Dose Modification for Toxicity: HD IL-2 and Hydroxychloroquine

Modification of the treatment protocol will occur by withholding doses of IL-2 rather than continuing therapy at a reduced dose. The only dose modification for patients of Hydroxychloroquine will be for those individuals deemed by the treating investigator as ‘likely’ due to hydroxychloroquine or the combination and not to IL-2 alone based on their experience and dose reduction as shown in **Table 5**. Missed doses of IL-2 will not be made up. Dose of IL-2 will be withheld for:

**9.2.1 Hypotension** refractory to fluids and pressors or requiring unacceptably high pressor doses (those associated with individual decrease in extremity perfusion). We will use vasopressors judiciously where necessary to support patients with limiting kidney/other organ perfusion. Requirement for vasopressors will be a relative indication for concluding a cycle (see 10.4.2.3 below).

**9.2.2 Anuria** for >24 hours and unresponsive to fluid replacement

**9.2.3 Respiratory distress** requiring oxygen >4 liters to maintain O2 saturation >95%.

**9.2.4 Confusion** (mental status changes can progress to paranoia despite discontinuation of IL-2; it is imperative that the IL-2 be stopped at any sign of persistent confusion or disorientation).

**9.2.5 Sustained ventricular tachycardia** or any sign or symptom of myocardial ischemia or myocarditis. Patients experiencing sustained ventricular tachycardia or myocardial ischemia should not receive further treatment with IL-2

**9.2.6 Metabolic acidosis** with HCO3 < 18, despite attempts to correct with IV HCO3.

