## **9.4 Management of Grade 4 Toxicity**

Patients with Grade 4 (Life Threatening) toxicity (with the exception of those Grade 4 toxicities listed in Section 10.5) may be treated with dexamethasone 4 mg qid until side effects improve to an acceptable level as indicated. Two dose reductions of hydroxychloroquine (Levels -1 and -2 in **Table 5**) may be allowed in a patient if treatment-limiting toxicity considered 'likely' attributable to the combination (and not to IL-2 alone) by the treating investigator is observed. A pill diary will be provided and is required.

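### Section 13.4 counts 39 patients for a 600 mg/d objective that at most 26 can inform, and its printed interval for 5/39 is wrong

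*Combined protocol and SAP*

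**What the plan says.** Sections 1.1 and 13.2.1 restrict the primary objective to patients given HCQ 600 mg/d. Section 13.1 sets total accrual at 39 and adds "The initial dose of HCQ will be 600 mg/day for all patients". Section 13.4 says that, provided no TLT arises and the trial is not closed early, 39 patients will serve the 600 mg/d objective. Its precision example is 5 responses in 39, described as what a doubling of a CR rate near 8% would produce, with an exact 95% interval of 0.07 to 0.34 and width 0.27.

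The dose history is elsewhere. Section 2.18 reports five patients treated at 600 mg and 13 at 1200 mg, with a further 21 being accrued to join the five at the lower dose. The Summary and Schema and Section 13.3.1 both confirm 21 new patients at 600 mg/d.

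On toxicity, Section 13.3.1 states "If one or more TLTs are observed, treatment will be de-escalated to IL-2+HCQ 400 mg/day". Section 13.1 gives the same rule and points to Section 9.2 for the definition: "treatment-limiting toxicities [TLTs], as defined in Section 9.2), dosing will continue at 600mg/d, otherwise, HCQ will de-escalate to 400 mg/d". Section 13.2.3 instead refers to Section 10.5 for TLTs, and Section 10.5 is duration of overall response.

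**The concern.** The trial estimates a proportion without a hypothesis test, so the precision statement in Section 13.4 is the whole justification of its size for the primary objective. If the patient count, the example and the interval in that statement are wrong, readers are told to expect a precision that the trial cannot deliver at the dose in question. Anyone filling the gap up to 39 would have to bring in patients treated at twice that dose.

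The TLT clause adds a smaller doubt. Section 13.4 makes its patient count depend on no TLT occurring, but Section 13.3.1 does not say what one TLT does to patients other than the one who had it.

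**Working it through.** **1. Headcount by dose** (Section 2.18; the 21 also in the Summary and Schema and Section 13.3.1)

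- Total: 5 (600 mg) + 13 (1200 mg) + 21 (600 mg) = 39, the accrual goal in Section 13.1.
- Starting at 600 mg/d: 5 + 21 = 26.
- Shortfall against Section 13.4: 39 − 26 = 13, or 13/39 = 33%.

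**2. The plan's own interval.** The exact (Clopper-Pearson) 95% limits for x responses in n are the 0.025 quantile of Beta(x, n − x + 1) and the 0.975 quantile of Beta(x + 1, n − x).

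- 5/39: Beta(5, 35) gives 0.043 and Beta(6, 34) gives 0.274; width 0.231. The plan prints 0.07 to 0.34, width 0.27.
- Other methods for 5/39 do not match either: Wilson 0.056 to 0.267, Wald 0.023 to 0.233, Jeffreys 0.051 to 0.258, exact 99% 0.029 to 0.322.
- Among exact 95% intervals with n from 15 to 60, only 6/35 rounds to the printed limits (0.066 to 0.336, width 0.271). The documents do not say where the printed limits came from.

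**3. The doubled rate**

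- 2 × 8% = 16%, and 0.16 × 39 = 6.24, so about 6 responses. 5/39 is 12.8%.
- Using the 8/95 cited in Section 13.3.2, 2 × 8/95 × 39 = 6.57, which is further from 5.
- 6/39: 0.059 to 0.305, width 0.247.

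**4. The attainable case**

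- 0.16 × 26 = 4.16 (4.38 using 8/95), so about 4 responses.
- 4/26: Beta(4, 23) gives 0.044 and Beta(5, 22) gives 0.349; width 0.305.
- Neighbouring outcomes: 3/26 gives 0.024 to 0.302 (width 0.277); 5/26 gives 0.066 to 0.394 (width 0.328).
- Against the printed width: 0.305/0.27 = 1.13. Against the correct width for the same rate in 39 patients: 0.305/0.247 = 1.24.

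**5. The TLT rule, read across sections**

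- *Attribution.* Section 9.2 is largely a list headed "Dose of IL-2 will be withheld for", but it also says "The only dose modification for patients of Hydroxychloroquine will be for those individuals deemed by the treating investigator" as having toxicity likely "due to hydroxychloroquine or the combination and not to IL-2 alone". Section 9.4 repeats the test: "attributable to the combination (and not to IL-2 alone) by the treating investigator is observed". Because Section 13.1 takes its definition from Section 9.2, the test is available by cross-reference.
- *Unit.* Sections 6.3.1.1, 9.2 and 9.4 describe reductions in individual patients. Section 13.1 also says "Toxicity and response will be monitored after every three patients", and Section 13.4 makes the available number conditional on no TLT. Both leave room for a cohort rule.
- *Definition.* Section 9.4 also cites 10.5 for toxicities, and Section 13.2 cites 14.3.1 for what is now 13.3.1. References one section too high suggest that Section 9.5, the discontinuation criteria, was meant in 13.2.3. That list differs from Section 9.2.

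**The case against.** The best defence of Section 13.4 is that 39 is the true total accrual and that Section 13.1 gives every patient a starting dose of 600 mg. The total is right. The starting dose cannot hold for all 39, because Section 2.18 records 13 patients at 1200 mg, and Section 13.4 attaches the number explicitly to the 600 mg/d objective.

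It can also be said that the practical loss is modest: 0.305 is about 13% wider than the printed 0.27, and the upper limits almost coincide (0.349 and 0.34). With no hypothesis test, no type I error or power is affected. This stands and limits the weight of the point. The 24% comparison uses 6/39, an interval that the plan never prints.

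A reader might infer something stronger from Section 13.3.1: that a single expected IL-2 toxicity would take the whole trial off 600 mg/d. For illustration, assumed per-patient TLT rates of 2%, 5%, 10% and 20% give a 35%, 66%, 89% and 99% chance of at least one TLT in 21, from 1 − (1 − q)^21. The documents do not support that reading. Section 9.2 confines any HCQ reduction to toxicity not due to IL-2 alone, several sections describe reductions patient by patient, and no TLT rate is given. If the rule is patient-level, all 26 still start at 600 mg/d, and Section 11.0 does not exclude patients from the response analysis for departures in drug administration.

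Nor should a reviewer choose the unit. Section 13.3 contains no other numerical toxicity rule, since Table 8 covers response only. Making the de-escalation patient-level would remove the one candidate for a cohort rule.

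**Conclusion.** The point holds for Section 13.4, whichever way the TLT rule is read. At most 26 patients, not 39, can start at 600 mg/d. The printed interval is not the exact interval for 5/39, and 5/39 does not represent a doubled CR rate. On the plan's own assumption of about 16%, the trial should expect about 4/26 with an exact 95% interval of 0.044 to 0.349, width 0.305, against a printed 0.27. The headcount and the 5/39 interval rest only on figures in the documents. The 4/26 example also takes the assumed doubling as given, and 26 is a ceiling, reached only if all 21 enrol and every patient meets the requirements for the response analysis.

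The TLT wording is a minor matter of clarity. The patient-or-cohort unit is unstated and the Section 10.5 reference is wrong, but the attribution test is already in Section 9.2.

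**What to change.** Restate Section 13.4 for at most 26 patients at 600 mg/d (the first 5 plus 21 new), with an example such as 4/26, exact 95% interval 0.044 to 0.349, width 0.305. State that the 13 patients treated at 1200 mg are not counted for this objective.

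In the same amendment, as clarification only:

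- In Sections 13.1 and 13.3.1, say whether de-escalation applies to the individual patient or to all later patients. The choice is the sponsor's.
- Note there that the attribution test in Section 9.2 applies.
- In Section 13.2.3, correct the reference to Section 10.5 (probably 9.5) and reconcile it with the Section 9.2 definition used in 13.1, so that one TLT definition serves both the rule and the tabulation.

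This is a text amendment with no added patients or procedures. The cost is a slightly less favourable stated precision. If the sponsor settles on a patient-level rule, any cohort-wide dose change would rest on the existing monthly safety committee review.

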**\*Complete Response (CR):**

Disappearance of all target lesions. Any pathological lymph nodes (whether target or non-target) must have reduction in short axis to < 10 mm. For patients with > 90% Partial Response defined as at least a 90% decrease in the sum of the LD of target lesions, taking as reference the baseline sum LD sustained for greater than one year will be scored as a CR (maximal patient benefit), given the difficulty of evaluating lesions in some instances.

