### **10.4 Confirmation**

The main goal of confirmation of objective response is to avoid overestimating the response rate observed. To be assigned a status of PR or CR, changes in tumor measurements must be confirmed by repeat assessments that should be performed no less than 4 weeks after the criteria for response are first met. In the case of SD, follow-up measurements must have met the SD criteria at least once after study entry at a minimum interval (in general, not less than 6-8 weeks) that is defined in the study protocol.

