## 11.0 PARTICIPANTS EVALUABLE FOR RESPONSE

Reporting of results:

Clinical Results: All patients included in the study will be assessed for response to treatment, even if there are major protocol treatment deviations or if they are ineligible. Each patient will be assigned one of the following categories:

- 1) complete response
- 2) >90% partial response
- 3) partial response
- 4) stable disease
- 5) progressive disease
- 6) early death from malignant disease (within 3 months of initiating therapy)
- 7) early death from toxicity
- 8) early death because of other cause
- 8) unknown (not assessable, insufficient data).

All patients who met the eligibility criteria and receive at least one week of IL-2 treatment will be included in the main analysis of the response rate. Patients in response categories 5-8 will be considered as failing to respond to treatment (disease progression). Thus, an incorrect treatment schedule or drug administration does not result in exclusion from the analysis of the response rate.

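### The binding futility rule in Section 13.3.2 gives no time at which a patient becomes evaluable, so immature response counts can raise the risk of a false halt

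*Combined protocol and SAP*

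**What the plan says.** Section 13.3.2 has the monitoring committee apply the stopping table "after every three patients become evaluable for response". If the count is at or below the bound, "the trial will be halted for lack of efficacy". Nothing makes this advisory, sets a minimum follow-up, pauses accrual or says how a pending response is treated. The text cites a Table 10 that does not appear; Table 8 is taken as the rule.

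Section 13.3.2 does not define evaluable. Section 11.0, on participants evaluable for response, says that eligible patients who "receive at least one week of IL-2 treatment will be included in the main analysis of the response rate". It also places unknown or insufficient data among the categories scored as failure. Section 4.4 uses a similar threshold, adding two weeks of HCQ.

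Section 6.4 puts the first scans at weeks 8 and 12 after the start of IL-2, each with a one-week window, and later scans after each course. Section 10.4 requires a PR or CR to be confirmed "no less than 4 weeks after the criteria for response are first met". Courses run to week 36. Under Section 10.3, a reduction of at least 90% that is "sustained for greater than one year will be scored as a CR".

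The counted event is stated in two ways in Section 13.3.2. One sentence halts "if the number of complete responses is less than or equal to the number in the right-hand column"; the Table 8 caption halts "if the number of partial or complete responses is less than or equal to the number in Column 2".

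Section 2.18 reports the first five patients at 600 mg/d, "with one patient deemed a complete response".

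**The concern.** A futility bound of this kind takes each counted patient as a success or a failure. If patients enter the count before a response could have been confirmed, they add to the denominator and cannot add to the numerator. The rule then reads immaturity as lack of effect.

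The text permits this. The one evaluability threshold is reached many weeks before the earliest confirmed response, and a patient without a scan would fall in the unknown category, which counts as failure. Because the halt is mandatory, a false signal would end the trial and cut short the estimate of the CR proportion, which is its primary objective.

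**Working it through.** **1. The plan's own bounds.** Inputs from 13.3.2: a prior from 8 CRs in 95 patients, taken as Beta(8,87), and a halt if P(rate < 0.10) > 0.8. With x responses in n patients the posterior is Beta(8+x, 87+n−x). The largest x that meets the criterion is:

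| n | Bound x | P at x | P at x+1 |
|---|---|---|---|
| 18 | 0 | 0.882 | 0.799 |
| 21 | 1 | 0.823 | 0.724 |
| 24 | 1 | 0.845 | 0.753 |
| 27 | 1 | 0.865 | 0.780 |
| 30 | 2 | 0.805 | 0.706 |
| 33 | 2 | 0.827 | 0.735 |
| 36 | 2 | 0.848 | 0.762 |

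All seven rows of Table 8 are reproduced. The n−x term shows the assumption: every counted patient who is not a response is a settled failure.

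**2. Earliest confirmed response.** Week 8 + 4 weeks = week 12, nominally. With one-week windows the two scans can be less than 4 weeks apart, so even the week-12 scan may leave a response unconfirmed.

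**3. Illustrative case.** Take the 600 mg/d patients only: 5 treated with 1 CR, plus 21 new patients. Row 18 (bound 0) cannot be met, since one response is already recorded. Row 21 (bound 1) halts if none of the 21 − 5 = 16 new patients has a recorded response. A trial that passes row 21 has at least 2 responses and cannot meet row 24 (bound 1). Row 21 therefore decides.

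Mature data:
- True CR 16% (Section 13.4, double the historical 8%): 0.84^16 = 0.061.
- PR+CR 25% (independent-review rate of the Select trial, Section 2.2): 0.75^16 = 0.010.

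**4. Effect of immature counts.** Assumed accrual is 21/15 = 1.4 to 39/15 = 2.6 patients a month, using the 15 months in 13.4. If the look comes one week after the 16th new patient starts IL-2 and every response is confirmed at day 84, that patient is unresolved. So are those who started in the preceding 84 − 7 = 77 days: on average (77/30.4) × 1.4 = 3.5 to (77/30.4) × 2.6 = 6.6 patients. About 16 − 1 − 3.5 = 11.5 down to 16 − 1 − 6.6 = 8.4 patients can then show a response. Roughly, 0.84^11.5 = 0.13 and 0.84^8.4 = 0.23. Simulation with Poisson accrual lets that number vary and gives slightly higher values. Spread means confirmation in equal thirds at weeks 12, 24 and 36 (assumed). Probability of a false halt:

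| Patient counted at | Confirmation | CR 16% | PR+CR 25% |
|---|---|---|---|
| Fully mature | – | 6% | 1% |
| One week of IL-2 | all at week 12 | 14–25% | 5–12% |
| One week of IL-2 | spread | 29–57% | 15–42% |
| Week 12 | all at week 12 | 6% | 1% |
| Week 12 | spread | up to 24% | up to 11% |

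Ranges run from 1.4 to 2.6 patients a month. Repeat runs differ by about one percentage point.

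**The case against.** The strongest reply is that Section 11.0 says who enters the response analysis, not when a monitoring look takes place. In ordinary usage a patient is evaluable for response once response has been assessed, which here means after the week 8 or week 12 scan. That stands. A reader might infer that the plan does count patients after one week of IL-2; the documents do not say so, and the one-week rows above show what the wording allows. At week 12 with confirmation by then, lag adds nothing, and any excess at that look comes from assumed late responses.

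It is also fair that the opening sentence of 13.3.2, its probability criterion and the caption rule all point to PR+CR, where the risk is smaller. A patient who later converts to CR would often already count as a PR. Accrual is uncertain too: the 15 months in 13.4 is a planning assumption for a survival interval, and slower accrual shrinks the effect.

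A reader might also pool all 18 earlier patients with the single reported CR and infer that a halt at row 21 is all but certain. The documents do not support this. Section 2.18 reports toxicity and one death among the 13 patients at 1200 mg/d and says nothing about their responses, so scoring them as no response treats silence as data.

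What the reply leaves untouched is that a mandatory rule has a trigger that can be read as week 1, week 8 or week 12, with no provision for pending responses.

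**Conclusion.** The point holds as a gap in the rule. Section 13.3.2 does not tie evaluability to an assessment time, and its bounds are valid only for resolved patients. In the 600 mg/d illustration, the chance of halting a regimen with a 16% CR rate goes from 6% to somewhere between 6% and 57%, depending on the reading and on response timing. With PR+CR at 25% it goes from 1% to between 1% and 42%. The upper ends need the one-week reading, late responses and the faster accrual together. Accrual and response timing are assumptions, and the case takes the five earlier 600 mg/d patients as counted.

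Lag is not the only source of false halts. Applied from the first patient over all seven rows with mature data, Table 8 halts 17% of the time at CR 16% and 2.4% at PR+CR 25%. Defining maturity removes only the lag part, and the size of what remains depends on which event is counted.

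**What to change.** Amend Section 13.3.2 in three places.

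1. State that, for Table 8, patients count in order of enrolment and only after the week-12 scan or earlier documented progression or death. Say that the one-week rule of Section 11.0 does not apply to this look.
2. State that the trial is not halted while recorded responses plus counted patients with a pending response exceed the bound. Pending means an unconfirmed response or, if CRs are the counted event, an ongoing PR that could still become a CR. The second part also covers the one-year route to CR.
3. State whether Table 8 counts CR or PR+CR, and make the text, the criterion and the caption agree.

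The hold should stay this narrow. If every unprogressed patient were pending until week 36, 92–100% of halts would come after enrolment had ended (simulated at true CR 8%, the same accrual range and an exponential median PFS of 4.3 months). The rule would then rarely spare any patient. The narrow hold still misses a late responder with no response at week 12.

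The cost is a change of wording. A true futility halt may come some weeks later, after more patients have been enrolled. If CRs are the counted event, an ongoing PR can hold the halt for longer.
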